A second alternative to traditional physical therapy is known as neuromuscular electrical stimulation (NMES). This technique, colloquially called “e-stim,” is used to engage the quadriceps muscle, which undergoes a dramatic weakening, up to a 60% loss of strength, following total knee arthroplasty [13]. In e-stim, electrodes are thus positioned around the thigh; many NMES technologies integrate these electrodes into a brace that the patient wears. The

electrodes then conduct electrical signals to the muscle, mimicking the nervous system's own action potentials and causing the muscle cells to contract. The level of stimulation increases with the intensity of the current, which can be controlled by the patient in today's NMES devices.

For patients who receive total knee replacements, combining e-stim therapy with physical therapy in the preoperative and early postoperative stages has been shown to reduce knee extensor lag, decrease length of stay, and improve short-term walking speed up to one year after surgery. One study found that electrical stimulation improved the American Knee Score and the Oxford Knee Score for patients six weeks out of surgery. Statistically significant changes in walking speed and functional recovery were both noted [14].

As mentioned above, we also know that one month after TKA, quadriceps muscle strength has typically dropped by about 50–60% of its preoperative levels [15]. This weakness tends to persist in the years following surgery, often causing loss of balance, falls, and greater difficulty with standing up or climbing stairs. Literature on the topic suggests that NMES may effectively (though not perfectly) attenuate the loss of quad strength and improve functional performance following total knee replacement [16–19]. Although the learning curve has required supplementary education at times, such devices are less expensive than physical therapy and would thus be a welcome alternative to PT if its effects are indeed comparable.

Overall, we propose a non-superiority treatment study that will compare our traditional standard of care (home visiting physical therapists) with telemedical home-based therapy and with e-stim technology.

II. SPECIFIC AIMS

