The purpose of this study is to investigate the superiority of telemedicine-guided physical therapy and e-stim devices in the first three weeks after a total knee replacement, compared with the current standard of care of home physical therapy. We propose equal outcome measures such as quadriceps strength, range of motion, proprioception, functional tests, and general outcome measures at 2–3 months following total knee replacement.

We propose that a decrease of cost for outpatient physical therapy by 50% without decreasing outcome by more than 10% would create value, but that any decrease in cost must not result in a decrease in outcomes.

III. SUBJECT ENROLLMENT

Subjects for this study include all patients who are aged 18 or older and electing to undergo unilateral total knee replacement (TKR) with [name] at Brigham and Women's Faulkner Hospital (BWFH) regardless of sex or other status.

Inclusion criteria:

- Age 18 or older
- Owns a device with internet connection

- Can download the E-vive application for the contractile garment (has sufficiently up-to-date phone or tablet, or has family member with such a device).
- Has a rudimentary understanding of Internet technology, especially e-mail
- Has a flexion of 90 ° and flexion contracture of 5 ° at the point of discharge
- Approved by a physical therapist to participate safely in the study at the time of discharge

Exclusion Criteria:

- Rheumatoid arthritis
- History of epilepsy
- Implanted and body-worn electronic medical device, including cardiac pacemakers, neural stimulators, insulin pumps, etc.
- Poor understanding of the use of the brace/electrical stimulation
- Lesions on the skin over the thigh
- Uncontrolled diabetes
- Uncontrolled hypertension
- Bilateral TKA or UKA planned
- If female, pregnant
- Cannot use non-operated leg postoperatively to propel active motion splint, caused by neurological or muscular diseases such as complete or incomplete paralysis or other causes of weakness with an inability to bend or extend knee
- Loss of sensation in operated or non-operated leg
- Has below- or above-knee amputations of non-operative leg
- Below- knee amputation of operated side
- Chronic pain syndrome with inability to walk
- Taking chronic narcotics and/or is taking more than 10mg codeine per day, or any Hydrocodone, or more than 200 mg of tramadol, or any other narcotics prescribed for moderate to severe pain
- Involved in pain clinics for chronic pain, or pain that is not related to the knee

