- Has been diagnosed with knee disorder other than osteoarthritis, post-traumatic osteoarthritis, gout, pseudo gout, or any inability to walk due to disorders unrelated to the knee (e.g., hip disorders, spinal stenosis, paralysis, hemi-paralysis)

V. STUDY PRODECURES

Patients who are undergoing total knee replacement (TKR) with [name] at Brigham and Women's Faulkner Hospital and meet all eligibility criteria will be informed about the study and asked if they would like to participate. The research assistant (RA) will screen upcoming surgeries and mail a letter describing the study to all qualifying patients to inform them of the study. If the patient has not contacted the study team within one week after this letter is mailed, the RA will call the patient by phone and ask whether the patient agrees to participate. Those who show interest will be offered the opportunity to discuss with both the RA and Principal Investigator (PI). Upon agreement, the patient's consent will be obtained and they will be randomly assigned to a treatment group using a computer-generated randomization.

A standardized mean difference of 0.90 has been reported in the previous published studies for quadriceps muscle strength between control and NMES intervention groups. This study will require 26 patients per group using this standardized mean difference, along with 80% power and the level of significance (p-value) set to 0.05. Adding in a 10% expected dropout rate, planned enrollment will be 29 patients per group for a total enrollment of 87 patients.

Approximately 2-3 months before surgery, patients will sign informed consent and will be randomly assigned to one of 3 treatment groups, to be described in detail below. Patients in all groups will receive a standardized telemedical “Pre-Hab” program (iGetBetter, Southborough, MA) to be followed in anticipation of surgery. This program includes both strengthening exercises and proprioception exercises. Prior to enrolling in the Pre-Hab program, all patients will undergo our standardized functional testing, including proprioceptive evaluation. The RA will also give each patient a live tutorial on how to use iGetBetter.

During their preoperative appointments, all patients will undergo preoperative testing to assess joint function and leg strength. Tests will measure sit-to-stand capabilities, quadriceps strength, distance walked in 2 minutes, walking speed, proprioception (balance), and range of motion.

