Before surgery, Patients in Group 1 (the first treatment group) will receive no treatment except for iGetBetter; this is the current preoperative standard of care. After surgery, Group 1 patients will be given a Post-Op program from iGetBetter to use for 2–3 months. For the first 3 weeks, patients will only use iGetBetter. After those 3 weeks have elapsed, the patient will receive outpatient physical therapy in addition to iGetBetter, approximately twice per week for the next 6–8 weeks as all other groups.

Before surgery, Patients in Group 2 (the second treatment group) will receive iGetBetter like the other groups. They will also receive CyMedica’s “E-vive” conductive garment and asked to download the corresponding smartphone application. They will be instructed to wear the e-stim garment two times each day, for 20 minute intervals each, for the 3 weeks immediately before surgery, and to change the electrodes weekly.

Stimulation from the garment will have the following parameters: frequency of 50 Hz; pulse duration of 5 ms; time on: 12.8 seconds; and time off: 10 seconds. The total contraction time in a 20-minute treatment will be 11 minutes. The waveform will be pulsed and asymmetrical.

Patients will be instructed on the proper use of the brace, including not to apply the two therapies consecutively to provide sufficient recovery time between sessions (recommended therapy is one session in the morning and one session in the afternoon/evening), and not to engage the NMES beyond what he or she can tolerate.

After surgery, Group 2 patients will immediately continue using the E-vive e-stim device, starting on the DOS. They will be taught how to use the device safely over their surgically repaired leg. For the first 3 weeks, they will only use the E-vive device, 2 times per day. After those 3 weeks have elapsed, the patient will receive outpatient physical therapy in addition to the E-vive home-based e-stim therapy, approximately twice per week for the next 6–8 weeks.

Before surgery, Patients in Group 3 (the control group) will receive no treatment except for iGetBetter; this is the preoperative standard of care. After surgery, Group 3 patients will receive the postoperative standard of care for total knee replacements at BWH. For the first 3 weeks, patients will receive home physical therapy. After those 3 weeks have elapsed, the patient will receive outpatient physical therapy approximately twice per week for the next 6–8 weeks.

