It is also possible that the E-vive group could have worse outcomes than the other two groups if the patients use the device too little or too much, or if they do not supplement the stimulation of the quad with stretches from outpatient physical therapy designed to improve range of motion. The device is linked through a smartphone to monitor compliance and range of motion. On rare occasions, E-vive therapy can result in skin reactions such as rash, inflammation, irritation, or electrode burns.

It is possible that the three groups may demonstrate different levels of postoperative outcomes and patient satisfaction — though we do not have a clear hypothesis as to which groups will yield the highest and lowest scores.

All risks and strategies for mitigation will be clearly explained during the consent process.

VIII. POTENTIAL BENEFITS

While no benefit to participation is ensured, it is possible that the patients in Group 1 may benefit from improvement of hip and knee strength and improved standing balance, and our preliminary unpublished results prove this. Patients are also tethered to [name] through their pain, satisfaction, and sleep reports. Patients in Group 2 might demonstrate similar increased muscle strength and similar range of motion compared to the other groups. Due to the established nature of PT, our current standard of care (Group 3) will show similar or better outcomes compared to Group 1 and Group 2 measured by our outcomes variables.

Results of this study may also help to improve treatment options for patients recovering from TKRs.

IX. MONITORING AND QUALITY ASSURANCE

Data which could indicate a potential complication, whether related to the study or not — such as heightened risk of adverse outcomes, insufficient range of motion on the operated joint, or inability to use the web-based program — will be addressed by the PI immediately and reported in accordance with PHRC guidelines. The PI will determine if the study should be altered in any way or stopped for safety reasons.

Reasons for stoppage include a rate of adverse events greater than 10% in either group. These checks will help to ensure validity and patient safety. Unanticipated problems and adverse events will be reported to the PHRC in accordance with PHRC guidelines.

X. REFERENCES

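### The 80% power claim rests only on an NMES-versus-control effect of 0.90 SD, so it is unsupported for telemedicine versus home therapy and unexplained for E-vive versus home therapy

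*Combined protocol and SAP*

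**What the plan says.** **Sample size (Section V, Study Procedures).** The effect size is given as: "A standardized mean difference of 0.90 has been reported in the previous published studies for quadriceps muscle strength between control and NMES intervention groups". The group size is then stated: "This study will require 26 patients per group using this standardized mean difference". Power is put at 80% and alpha at 0.05. Enrolment allows for losses: "Adding in a 10% expected dropout rate, planned enrollment will be 29 patients per group for a total enrollment of 87 patients". The paragraph names no test, no sidedness, no multiplicity rule and no comparison to which the power belongs.

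**Treatments (Section V).** Group 1 uses telemedicine exercises alone for the first three postoperative weeks, and Group 3 has home physical therapy. Neither description includes e-stim at any time. For Group 2 after surgery: "For the first 3 weeks, they will only use the E-vive device, 2 times per day". Group 2 also has e-stim added to the telemedicine programme in the three weeks before surgery, and alongside outpatient therapy after week 3.

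**Background (Section I).** The e-stim evidence includes this statement: "combining e-stim therapy with physical therapy in the preoperative and early postoperative stages has been shown to reduce knee extensor lag".

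**Expected result.** Section II gives a superiority purpose for both alternatives over home therapy, and its next sentence reads in part "We propose equal outcome measures such as quadriceps strength". Section VIII adds: "Patients in Group 2 might demonstrate similar increased muscle strength and similar range of motion compared to the other groups".

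**Analysis (Section VI).** The three groups are compared for a statistically significant difference, with a 5% type I error rate for all analyses.

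**The concern.** A power statement holds for a particular comparison, test and assumed difference. Here one difference, between NMES and control, sets the size of all three groups, and the resulting 80% reads as a property of the whole study.

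- **Telemedicine versus home therapy.** Neither arm has e-stim, so an NMES effect says nothing about the difference to expect. The documents give no other effect size for this comparison.
- **E-vive versus home therapy.** In postoperative weeks 1–3, the period named in the aim, e-stim stands in place of home therapy. The protocol does not argue that 0.90 SD carries over to an active comparator of this kind.
- **Expected result.** A planning difference of 0.90 SD cannot be held together with a proposal of equal quadriceps strength.

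What is at stake is how a null result will be read. The analysis section looks only for significance, while other sections hope for equal or similar outcomes. A reader who believes the study had 80% power throughout could take a non-significant difference as evidence that home therapy can be dispensed with.

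**Working it through.** **Inputs.** Standardized difference d = 0.90, power 80%, alpha 0.05, n = 26 evaluable per group, 10% dropout (all Section V). Two-sided testing is assumed because sidedness is not stated.

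**1. Reproducing 26, 29 and 87.** For two means, n per group = 2(z₁₋α/₂ + z₀.₈₀)² / d².
- Alpha 0.05: 2(1.960 + 0.842)² / 0.81 = 19.4, so 20 (21 by t-test).
- Alpha 0.05/3: 2(2.394 + 0.842)² / 0.81 = 25.8, so 26 (28 by t-test).
- Three-group ANOVA at 5% with means 0, 0.45 and 0.90 SD: 25.
- Dropout: 26 / 0.90 = 28.9, so 29; 3 × 29 = 87.

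The 26 can thus be reached, but not by the plain two-group formula at 5%, and the protocol does not say which method it used. The arithmetic is not in dispute; the question is what the 0.90 applies to.

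**2. Power if a 0.90 SD difference is real.** For a t-test with 26 per group, df = 50 and the noncentrality is d√(n/2) = 0.90 × √13 = 3.245.
- Two-sided 5% (critical t 2.009): 89%.
- Two-sided 0.05/3 (critical t 2.477): 78%.

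For the three-group ANOVA at 5%, df = 2 and 75, and λ = n Σ(mᵢ − m̄)².
- Third mean halfway between the other two: λ = 26 × 0.405 = 10.53, power 82%.
- Third mean equal to one of the other two: λ = 26 × 0.54 = 14.04, power 92%.

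**3. Power at smaller differences.** Same t-test, 26 per group.

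| True difference (SD) | Alpha 0.05 | Alpha 0.05/3 |
|---|---|---|
| 0.90 | 89% | 78% |
| 0.70 | 70% | 52% |
| 0.50 | 42% | 26% |
| 0.30 | 19% | 9% |

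The smallest difference detectable with 80% power is 0.79 SD at 5% and 0.92 SD at 0.05/3.

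**4. Precision.** The 95% half-width for a pairwise difference is t₀.₉₇₅,₅₀ × √(2/n) = 2.009 × √(2/26) = 2.009 × 0.277 = 0.56 SD. An observed difference of zero would leave true differences of up to about half an SD in either direction compatible with the data.

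**5. Matching the input to the comparisons.**

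| Comparison | E-stim contrast? | Basis for 0.90 SD in the documents |
|---|---|---|
| Telemedicine vs home therapy | No | None |
| E-vive vs home therapy | Yes, but e-stim alone against home therapy in postoperative weeks 1–3 | Cited, transfer not explained |
| E-vive vs telemedicine | Yes | Cited, transfer not explained |

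**The case against.** The strongest reply is that Section VI describes a comparison of three groups, for which an overall test is a natural reading. On that reading the study has 82–92% power whenever one pair differs by 0.90 SD and the third mean lies at or between the other two. No telemedicine effect is then needed. This stands as far as it goes: a study-level power claim can be defended if the overall test is named and the 0.90 SD is attached to the E-vive group. It still gives no power for telemedicine versus home therapy, and a significant overall test does not say which pair differs.

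Other parts of the defence also stand.
- E-stim replaces therapy only in postoperative weeks 1–3. Before surgery and after week 3 it is an addition, and strength is tested at 2–3 months.
- The background sentence on e-stim combined with therapy concerns extensor lag, length of stay and walking speed, not strength. The documents do not say whether the studies behind 0.90 tested e-stim as an addition to therapy.
- Equal strength is one of several conflicting expectations. Section II also states superiority, Section I non-superiority, Section VII no clear hypothesis, and Section VIII a control group that does similarly or better.

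Three stronger readings are tempting and should not be adopted.
- A reader might infer that the comparisons lack 80% power. That depends on true differences that the documents do not give.
- A reader might infer that all three pairwise differences were set at 0.90 SD. Section V cites one contrast only; the match at 0.05/3 is a back-calculation, not a stated method.
- A reader might turn the 10% loss of outcome in Section II into a non-inferiority margin and compute power for it. That figure sits in a statement about cost and value, no SD is given to convert it, and Section VI plans no such test.

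**Conclusion.** The concern holds as a matter of support. The 80% power statement has no basis for telemedicine versus home therapy. For E-vive versus home therapy it rests on an unexplained transfer of 0.90 SD, and it conflicts with the proposal of equal quadriceps strength. As a claim about the whole study, the paragraph is wrong as written. Actual power below 80% is not established: for a two-sided 5% t-test, power is at least 80% for any true difference of 0.79 SD or more.

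The practical consequence is certain whatever the true effects are: with a half-width of about ±0.56 SD, a non-significant result cannot be read as equality. These figures assume 26 evaluable patients per group, a common SD, two-sided tests and unadjusted comparisons of quadriceps strength.

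**What to change.** Keep 29 per group and change two sections.

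**Section V, sample size.**
- State that the power claim is conditional on a true 0.90 SD difference in quadriceps strength involving the E-vive group, and explain why that figure is taken to apply against home therapy.
- Name the test and alpha to which the claim refers, and give the matching power at 26 per group: 89% for a two-sided 5% t-test, 78% at 0.05/3, or 82–92% for a three-group ANOVA depending on the third mean.
- For telemedicine versus home therapy, state that no effect size was assumed. Give the difference detectable with 80% power (0.79 SD at 5%, 0.92 SD at 0.05/3) and the expected 95% half-width (about ±0.56 SD).

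**Section VI, analysis.** Add that each pairwise difference will be reported with its confidence interval, and that a non-significant difference will not be reported as equal or comparable outcomes.

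**Cost.** Rewording only, with no extra patients. The stated power becomes less favourable, and the trial gives up claims of equality that its precision cannot carry.

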Patients in all groups will attend two routine follow-up visits. The first will occur one week after surgery; there patients will have their dressing changed and receive narcotic prescriptions. At the second follow-up, which will occur 2–3 months after surgery, patients will receive the functional testing described above. We will also calculate total cost of the three different treatment modalities.

Additional routine data — including postoperative complications for infection, readmission rates, and routinely collected functional outcome measures — will be recorded at this 2- to 3-month visit. For all groups, the standard of care is to administer an opioid consumption diary in which patients submit VAS scores for pain, nausea, and satisfaction. The PI will review this diary with the patient during the first postoperative visit, and then again at the second. We will measure patients' pain, both in terms of VAS scores and in terms of total pain medications consumed. Each of these measures will be used for analysis at the completion of the study.

VI. BIOSTATISTICAL ANALYSIS

We will be comparing the three separate groups in the trial to see whether there exists a statistically significant difference between them. Variables in which we are interested are all detailed in the previous section. When comparing the three branches, all analyses will be run at a type I error rate of 5%.

VII. RISKS AND DISCOMFORTS

It is possible that the iGetBetter group could have worse outcomes than the other two groups if a patient does not log into the program, or does too many (or too few) of the exercises prescribed. However, our current experience is a high compliance rate with iGetBetter exercises and good hip and knee strength and standing balance 2 months after total knee replacement. Risks associated with a web-based rehabilitation program will be minimized by closely monitoring all information recorded by the patient. If patients are recording high pain scores or not recording exercises, the PI will be notified and the RA will contact those patients.

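### Section VI does not say whether or how the preoperative functional tests enter the analysis; adjusting for a value taken before Group 2 starts e-stim would be a cheap, optional gain in precision

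*Combined protocol and SAP*

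**What the plan says.** Section VI (Biostatistical Analysis) gives the whole analysis in three sentences. The main one is "We will be comparing the three separate groups in the trial to see whether there exists a statistically significant difference between them". The other two point to Section V for the variables and set the type I error rate at 5%. No test, model, covariate, baseline or change score is named.

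Section V (Study Procedures) describes testing before surgery in two places:

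- Before Pre-Hab: "Prior to enrolling in the Pre-Hab program, all patients will undergo our standardized functional testing". Proprioception is the only component named there.
- At preoperative appointments: "During their preoperative appointments, all patients will undergo preoperative testing to assess joint function and leg strength". The list follows directly: "Tests will measure sit-to-stand capabilities, quadriceps strength, distance walked in 2 minutes", then walking speed, proprioception and range of motion, six measures in all. These appointments are not dated relative to surgery.

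On timing, Section V states: "Approximately 2-3 months before surgery, patients will sign informed consent and will be randomly assigned to one of 3 treatment groups". Group 2 alone then wears the e-stim garment "for the 3 weeks immediately before surgery". At the visit 2–3 months after surgery, "patients will receive the functional testing described above".

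**The concern.** The same functional measures are planned before and after surgery in every patient, yet the analysis section gives the earlier value no role. Two things follow.

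1. **Precision.** A comparison of 2–3 month scores alone carries between-patient variation that a preoperative score would partly explain. With 26 patients per group, wider intervals are a real cost.
2. **An open choice of baseline.** If an analyst later decides to adjust, nothing says which test to use. Quadriceps strength, the variable behind the sample size, is listed explicitly only after the preoperative-appointment sentence, so that test would be the natural pick. If it was taken after Group 2 had begun e-stim, it is no longer a pre-treatment value for that group.

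The issue in the second item is testing after treatment has begun to differ, not testing after randomisation. Patients are randomised 2–3 months before surgery, so every preoperative test may follow randomisation.

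**Working it through.** **Inputs from the documents.** Standardised mean difference 0.90, 80% power, significance level 0.05, 26 per group, 10% dropout, 29 per group and 87 in total (Section V). E-stim in Group 2 starts 3 weeks before surgery; outcomes are measured 2–3 months after it.

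**Assumed inputs.** The baseline-outcome correlation r is not in the documents; 0.2 to 0.7 is used. The preoperative e-stim gain g is also not given; 0.2 and 0.4 SD are used for illustration.

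**Step 1: the plan's own figure.** The two-group formula is n = 2(z_α + z_β)² / 0.90².

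- Two-sided 0.05, 80% power: 2 × (1.960 + 0.842)² / 0.81 = 19.4, so 20 (21 with the t distribution).
- Two-sided 0.05/3, 80% power: 2 × (2.394 + 0.842)² / 0.81 = 25.9, so 26.
- A one-way ANOVA with the third group midway gives 25. Two-sided 0.05 at 90% power also gives 26.

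The stated 26 can therefore be reached, but only under a reading that the plan does not spell out. Dropout: 26 / 0.9 = 28.9, so 29; 3 × 29 = 87. The 26 is taken as given below.

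**Step 2: precision.** For one pairwise comparison with outcome SD = 1:

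- Unadjusted half-width = t(50 df) × √(2/26) = 2.009 × 0.277 = 0.557 SD.
- ANCOVA multiplies the variance by (1 − r²) × [1 + 1/(2n − 4)]. The bracket allows for chance baseline imbalance and equals 1 + 1/48 = 1.021.
- Adjusted half-width = t(49 df) × √(2/26) × √(variance ratio), with t = 2.010.

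| r | 1 − r² | × 1.021 | Variance cut | Half-width (SD) | Equivalent unadjusted n per group (26 / ratio) |
|---|---|---|---|---|---|
| 0.2 | 0.96 | 0.980 | 2% | 0.55 | 26.5 |
| 0.3 | 0.91 | 0.929 | 7% | 0.54 | 28.0 |
| 0.5 | 0.75 | 0.766 | 23% | 0.49 | 33.9 |
| 0.7 | 0.51 | 0.521 | 48% | 0.40 | 49.9 |

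Break-even is r = √(1 − 1/1.021) ≈ 0.14; below that no gain is expected.

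A plain change score is not an equivalent remedy. With equal SDs its variance is 2(1 − r), which exceeds the unadjusted variance whenever r is below 0.5.

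**Step 3: why the timing of the baseline matters.** If e-stim has already raised Group 2's baseline by g (in SDs of that test), ANCOVA removes r × g outcome SDs from the Group 2 effect. A simulation of 4,000 two-group trials per setting, 26 per group, true effect 0.90, gave:

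| r | g | r × g | Mean estimate, baseline inside the e-stim window | Mean estimate, baseline before e-stim |
|---|---|---|---|---|
| 0.3 | 0.2 | 0.06 | 0.845 | 0.905 |
| 0.3 | 0.4 | 0.12 | 0.777 | 0.898 |
| 0.5 | 0.2 | 0.10 | 0.798 | 0.897 |
| 0.5 | 0.4 | 0.20 | 0.699 | 0.899 |
| 0.7 | 0.2 | 0.14 | 0.758 | 0.899 |
| 0.7 | 0.4 | 0.28 | 0.621 | 0.902 |

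The unadjusted mean estimate was 0.90 to 0.91 throughout. Leaving baseline out costs precision, while using a baseline already changed by treatment shifts the estimate.

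Groups 1 and 3 receive the same preoperative care (iGetBetter only), so the later test does not have this problem in a comparison between those two.

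**The case against.** **Section VI is silent; it does not exclude baseline.** This stands. Section VI refers to all the variables of Section V, which include the preoperative tests, so an adjusted analysis would fit the text. A reader might infer that the plan has decided on an unadjusted analysis, but the documents do not support that. What remains is that the choice is unspecified and could be made after the data are seen.

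**The bias belongs to an analysis that nobody has proposed.** Also fair. A reader might infer that the planned comparison is biased. It is not, on this account: the shift in Step 3 needs a separate later test, taken in the 3-week window, used as baseline, and a Group 2 effect meant to include preoperative e-stim. The documents state none of these, and Section V can be read as describing one battery. The point is a condition on the fix, not a defect in the current text.

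**The gain may be negligible.** Correct at the low end. The pre-Pre-Hab test and the outcome are roughly 4–6 months apart (2–3 months before surgery plus 2–3 after) with an operation between, so r may be low.

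**Does precision matter more because of the 10% figure in Section II?** Section II includes "We propose equal outcome measures such as quadriceps strength, range of motion" among its aims and mentions an outcome loss of up to 10%, so one might treat 10% as a margin that the interval must exclude. The text does not carry that. The figure is part of a statement about value for cost, the same sentence goes on to rule out any worsening of outcomes from cost savings, and Section VI plans tests for difference.

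**Is power already ample?** About 89% at a standardised difference of 0.90 holds only for a single pairwise test at two-sided 0.05. At 0.05/3 it is about 78% (t distribution). The plan does not say which applies, so no general statement about spare power is warranted.

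**Conclusion.** The point holds as an optional precision improvement. Section VI leaves the role of the preoperative tests unstated, and a better use of largely planned data is available. At 26 per group the half-width would fall from 0.56 SD to between 0.55 and 0.40 SD for r between 0.2 and 0.7. All of that range rests on an assumed correlation, and at r = 0.2 the gain is trivial.

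The statement that leaving baseline out causes no bias concerns that omission only. It does not vouch for the rest of Section VI, which names no test or analysis set, or for the handling of patients who are randomised before surgery but fail the discharge criteria in Section III.

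The gain applies to the repeated functional measures. It does not extend to cost, complications, readmission or opioid use.

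**What to change.** In Section VI, add:

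> Each functional outcome at 2–3 months will be compared between groups by ANCOVA with treatment group and, as covariate, the value of the same measure from the testing done before Pre-Hab. A test taken after Group 2 has started e-stim will not be used as the baseline in comparisons involving Group 2.

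In Section V, confirm that the pre-Pre-Hab session includes all six listed measures, since only proprioception is named there. It would also help to state whether the two descriptions of preoperative testing refer to one battery or two, and when each takes place.

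**Cost.** Cheap, but not necessarily free: one degree of freedom per model and, if the pre-Pre-Hab session does not already include them, up to five listed tests added at that planned session. No extra visit or patient is needed.
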